4.1.1 Primary efficacy variables

The primary efficacy variables for this study are:

- Quantitative measurement of TUV_{joint} (all arms) and TUV_{global} (Arms 2 and 3 only)
- CDAI scores at baseline, 12 (± 1) weeks and 24 (± 1) weeks (Arm 3 only)
- DAS28 scores at baseline, 12 (± 1) weeks and 24 (± 1) weeks (Arm 3 only)
- ACR Response Criteria at 12 (± 1) weeks and 24 (± 1) weeks (Arm 3 only).

The primary efficacy variables of this study in Arms 1 and 2 are:

- The camera-specific precision of TUV_{joint} and TUV_{global} in subjects with active RA and healthy controls, which is defined as the Root Mean Square Difference (RMSD) between the consecutive 15-minute planar images.
- The stability of the mean/variance relationship, which is assessed by comparing the Coefficient of Variation (CV) of TUV_{joint} and TUV_{global} in subjects with active RA and healthy controls.

An added primary variable in Arm 2 only is:

- The longitudinal (8-day) precision of TUV_{joint} and TUV_{global} in subjects with active RA, which is defined as the RMSD of the TUV between the baseline and 8 day image at the same time point.

The primary endpoints in Arm 3 are:

- The Kendall rank correlation of $\Delta TUV_{global[5w]}$ with the response to new anti-TNF α bDMARD therapy defined as $\Delta CDAI_{12w}$ and $\Delta CDAI_{24w}$ (overall scores only) in study arm 3.
- The Kendall rank correlation of $\Delta TUV_{global[5w]}$ with the response to new anti-TNF α bDMARD therapy defined as the changes from baseline in DAS28 and in each of the ACR Response Criteria components at 12 (± 1) weeks and at 24 (± 1) weeks in study arm 3.

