9.3 Efficacy Variables

The efficacy variables for this study are defined below:

- Quantitative determination of TUV_{joint} and TUV_{global}
- Qualitative (i.e., visual) evaluation of SPECT/CT in detecting localization within synovial spaces of the bilateral hands and wrists
- Subject RA status as summarized in the CDAI and ACR Response Criteria overall score and their constituent sub-scores

It is presumed that the presence of radiotracer uptake for a joint indicates the presence of activated macrophages. The use of the term “localization” is synonymous with radiotracer uptake.

The efficacy endpoints for this study, by arm, are as follows:

Primary Endpoint(s)

ARMS 1-2

- The camera-specific precision of TUV_{joint} and TUV_{global} in subjects with active RA and HCs, which is defined as the Root Mean Square Difference (RMSD) between the consecutive 15-minute planar images.

- The stability of the mean/variance relationship, which is assessed by comparing the Coefficient of Variation (CV) of TUV_{joint} and TUV_{global} in subjects with active RA and HCs.

ARM 2

- The longitudinal (8-day) precision of TUV_{joint} and TUV_{global} in subjects with active RA, which is defined as the RMSD of images at the same time point.

ARM 3

- The correlation of $\Delta TUV_{global[5w]}$ and response to new anti-TNF α bDMARD therapy defined by the change from baseline (CFB) of CDAI to 12 ± 1 weeks and 24 ± 1 weeks ($\Delta CDAI_{12w}$ and $\Delta CDAI_{24w}$, respectively). The correlation of $\Delta TUV_{global[5w]}$ and response to new anti-TNF α bDMARD therapy from baseline to 12 ± 1 weeks and 24 ± 1 weeks defined by ACR Response Criteria (ACR $_{12w}$ and ACR $_{24w}$, respectively).

Secondary Endpoint(s)

ARMS 1-2

- The temporal stability of the 150 mcg tilmanocept mass dose/10 mCi radiolabeling dose.

ARM 1

- The normal ranges of TUV_{joint} in HC subjects, which is defined as the 5 and 95 percentiles of:
 - TUV_{joint} of bilateral joints (i.e., bilateral wrists, MCPs, PIPs, knees, elbows, shoulders)

ARM 2

- The qualitative evaluations of SPECT/CT in detecting localization within synovial spaces of the bilateral hands and wrists.

ARM 3

- The correlation of the $TUV_{global[0week]}$ and response to new anti-TNF α bDMARD therapy defined by the change from baseline (CFB) of CDAI to 12 ± 1 weeks and 24 ± 1 weeks ($\Delta CDAI_{12w}$ and $\Delta CDAI_{24w}$, respectively) and by ACR Response Criteria (ACR $_{12w}$ and ACR $_{24w}$, respectively).

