9.5.3 Analysis of Efficacy Variables

All efficacy analyses will be conducted on both the ITD and PP populations. The ITD population will be the primary analysis set.

9.5.3.1 Primary Endpoints Arms 1- 2

Precision endpoints will be assessed estimating the mean, standard deviation, n, minimum, median, and maximum of the signed differences, calculated as change from the initial measurement. The RMSD will be calculated and a 95% confidence interval on its value will be provided.

Stability of the mean/variance relationship will be assessed by the coefficient of variation of the differences for active RA subjects and HC subjects at 60 minutes and 180 minutes. 95% confidence intervals for the difference in CVs following the methods of ([Forkman 2009](#)) and from the bootstrap sampling distribution of the difference of the CVs will be provided based on N = 5000 bootstrap samples.

9.5.3.2 Secondary Endpoints Arms 1- 2

The normal ranges of ΔTUV_{joint} will be estimated from data collected from HC subjects (Arm 1 only) at 60 minutes and 180 minutes post-injection. The mean, standard deviation, n (number of joints), and quantile regression estimates of the 5 and 95 percentiles will be provided for shoulder, elbow, wrist, MCP, PIP, and knee.

9.5.3.3 Primary endpoint Arm 3

The Kendall rank correlation between $\Delta TUV_{global[5w]}$ with $\Delta CDAI_{12w}$ and $\Delta CDAI_{24w}$ will be computed and a 95% confidence interval for its value will be computed using Fisher's Z-transformation. Similarly, the Kendall rank correlation between $\Delta TUV_{global[5w]}$ with ΔACR_{12w} and ΔACR_{24w} (overall scores only) will be computed and a 95% confidence interval for its value will be computed using Fisher's Z-transformation.

9.5.3.4 Secondary endpoint Arm 3

The Kendall rank correlations between $\Delta TUV_{global[5w]}$ with the subscores of ΔACR_{12w} and ΔACR_{24w} (including tender joint count, swollen joint count, Patient assessment of global disease activity, Rheumatologist assessment of global disease activity, Patient assessment of pain, Patient assessment of physical function, Acute-phase reactant value) will be computed and a 95% confidence interval for its value will be computed using Fisher's Z-transformation.

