The Kendall rank correlations between $TUV_{global[0w]}$, $\Delta TUV_{global[12w]}$, $\Delta TUV_{global[24w]}$ with the $\Delta CDAI_{12w}$, $\Delta CDAI_{24w}$, ΔACR_{12w} , ΔACR_{24w} will be computed and a 95% confidence interval for their values will be computed using Fisher's Z-transformation.

Additional efficacy analyses may be described in the Statistical Analysis Plan (SAP) for the study.

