The Kendall rank correlation between $\Delta TUV_{global[5w]}$ with $\Delta CDAL_{12w}$ and $\Delta CDAL_{24w}$ will be computed and a 95% confidence interval for its value will be computed using Fisher's Z-transformation. Similarly, the Kendall rank correlation between $\Delta TUV_{global[5w]}$ with changes from baseline in DAS28 and in each of the ACR Response Criteria components at weeks 12 and 24 will be computed and a 95% confidence interval for its value will be computed using Fisher's Z-transformation. The marginal distributions of the variables will be characterized with the mean, standard deviation, and the number of data pairs.

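### The SAP never computes the protocol-primary Arm 3 correlations of 5-week TUV_global change with overall ACR response, and makes ACR components and DAS28 primary instead, with no reason in the supplied documents

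*SAP*

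**What the plan says.** **Protocol.** Section 9.3 makes primary for Arm 3 the correlation of 5-week TUV_global change with CDAI change, and with response at 12 and 24 "weeks defined by ACR Response Criteria". Section 9.5.3.3 gives the analysis: a Kendall correlation with a 95% interval by Fisher's Z. For ACR it is restricted to the overall result ("overall scores only) will be computed"). The seven constituents come under Secondary endpoint Arm 3, in 9.5.3.4 ("including tender joint count, swollen joint count, Patient assessment of global disease activity", and so on). The clinical efficacy variable in 9.3 is "Subject RA status as summarized in the CDAI and ACR Response Criteria overall score and their constituent sub-scores", with no mention of DAS28.

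**SAP.** The Introduction says the plan is consistent with Amendment 4. Section 4.1.1 lists ACR Response Criteria at Weeks 12 and 24 among the primary efficacy variables. Its second Arm 3 primary endpoint, however, is response "defined as the changes from baseline in DAS28 and in each of the ACR Response Criteria components at 12" and 24 weeks. The restriction to overall scores does appear in 4.1.1, but it is attached to CDAI. Section 4.2.1 repeats the choice: the 5-week TUV change "with changes from baseline in DAS28 and in each of the ACR Response Criteria components at weeks 12 and 24 will be computed". Footnote a to the Table 19 shell says that ACR change is evaluated through its components. The same footnote stands under Tables 21 and 23.

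The SAP still uses overall ACR in other places: the Table 42 frequencies, the secondary concordance tables against TUV (Tables 44-61) and Figures 1-3.

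**The concern.** The protocol fixes what the primary result of Arm 3 is, and the SAP fixes what is programmed. If the SAP is followed, the report will carry a primary section without half of the protocol's primary correlations. It will carry 16 others under the same label. A reader could not tell from the report that a planned primary analysis had not been run, because the SAP declares no departure.

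The SAP is also at odds with itself. It names ACR response as a primary variable and gives it no primary analysis. Component correlations are not a substitute: each describes one constituent, and none says whether TUV change tracks the composite response that the protocol named.

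**Working it through.** **Count.** The documents state no number of primary correlations, so there is no figure to reproduce. The count comes from the text.

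| 5-week TUV_global change with | Protocol 9.3, 9.5.3 | SAP 4.1.1, 4.2.1 |
|---|---|---|
| CDAI change, Weeks 12 and 24 | primary, 2 | primary, 2 |
| Overall ACR response, Weeks 12 and 24 | primary, 2 | not computed, 0 |
| Seven ACR components, Weeks 12 and 24 | secondary, 7 x 2 = 14 | primary, 14 |
| DAS28 change, Weeks 12 and 24 | in no endpoint, 0 | primary, 2 |
| **Primary total** | **2 + 2 = 4** | **2 + 14 + 2 = 18** |

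SAP 2.5 forbids pooling of readers and refers to three of them. Applied to both sides, that gives 4 x 3 = 12 against 18 x 3 = 54. Of the SAP's 18, only 2 are primary in the protocol.

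**Tables.** Tables 19-24 have rows for CDAI overall, CDAI components, ACR components and DAS28. They have no row for overall ACR. The gap therefore also takes in the protocol's secondary correlations of overall ACR with baseline, 12-week and 24-week TUV.

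**Authority for the change.** Protocol 9.5.3.4 says "Additional efficacy analyses may be described in the Statistical Analysis Plan (SAP) for the study". That covers additions such as DAS28. It does not cover leaving out a primary analysis. The SAP revision history has two entries, both on the TUV prediction algorithms.

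**Can the missing correlation be computed as the protocol writes it?** Not without a definition. Protocol 9.5.3.3 correlates a change in ACR, but ACR response is already an improvement from baseline (8.3.4), and Appendix 8 calls it dichotomous. SAP 4.2.2 already derives the highest level reached (none, 20, 50 or 70), which is ordinal and usable. It is heavily tied. Against an untied measure, the largest attainable tau-b is about sqrt(1 - sum of squared level proportions). Two illustrative splits, which are assumptions:

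- 40/25/20/15%: sum of squares 0.285, ceiling sqrt(0.715) = 0.85.
- 50/25/15/10%: sum of squares 0.345, ceiling sqrt(0.655) = 0.81.

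The interval method should therefore be chosen with ties in mind.

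**Lesser inconsistencies found on the way.**

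- SAP 4.1.2 lists as secondary two items that 4.1.1 makes primary: 5-week TUV change with CDAI change, and with the Week 24 components. SAP 2.5 covers Week 12 only and omits DAS28.
- Protocol 9.5.3.4 plans correlations of baseline TUV_global with CDAI and ACR response, for which a 95% "confidence interval for their values will be computed". SAP 4.1.2 lists the endpoint, but 4.2.2 and Tables 19-24 do not compute it.
- Camera-specific precision (RMSD of A against B scans) is primary for Arms 1-2 and has a method in SAP 4.2.1, but no table among Tables 1-67. It is marked as completed at Interim Analysis 3, one purpose of which was to optimise the TUV metric (SAP 2.4). The SAP does not say whether that analysis used the final metric and all Arm 1-2 subjects.

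**The case against.** The best defence is that ACR has not been dropped. It remains a listed primary variable, is tabulated, is plotted, and is compared with TUV at each of the 20, 50 and 70 levels. DAS28 also belongs in the trial: the third primary objective speaks of clinical assessments in general, and protocol 8.3.2 schedules DAS28 in Arm 3 at Weeks 5, 12 and 24. And the protocol's own ACR variable is undefined, so the SAP authors may have turned to quantities they could compute. All of this stands. It explains the SAP's choices but does not supply the missing analysis, and it makes only the primary label of DAS28 questionable, not its inclusion.

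Four stronger readings are tempting, and the documents do not support them.

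- *The concordance tables lose power against the correlation.* Both documents plan Arm 3 correlations as estimates with 95% intervals, with no test or success rule. A power comparison would need tests that neither document plans, and it would ignore the component and DAS28 correlations that the SAP puts in their place.
- *Eighteen primary correlations inflate the error rate.* With no test or significance level attached to them, there is no error rate to inflate.
- *The components are redundant because they repeat CDAI.* Eight of the 14 do use CDAI's four inputs, but overall ACR uses those inputs too. The other six (pain, function and acute-phase reactant at two visits) lie outside CDAI.
- *Interim data drove the change.* SAP 2.4 reports Interim Analysis 3 in the past tense, so version 1.1 follows a look at Arm 3 data. But version 1.0 and the interim analysis plans are not among the supplied documents, and nothing shows when or why the endpoints changed.

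**Conclusion.** The point holds. Two of the four protocol-primary Arm 3 correlations are absent from the SAP's text and tables. Sixteen correlations that the protocol does not call primary take that label, in a document that claims consistency with the protocol. This should be corrected before the final analysis. It rests on a direct comparison of current texts and on no modelling. The absence of a reason is established only for the documents supplied. The inconsistent labels, the missing baseline TUV rows and the untabulated A-against-B precision are smaller matters. The last may need only a clarifying statement.

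**What to change.** 1. Add to SAP 4.1.1 and 4.2.1, and to Tables 19-20, Kendall tau-b with a 95% interval for 5-week TUV_global change with overall ACR response at Weeks 12 and 24. Name the variable. The ordinal level derived for Table 42 is suitable. Beside the protocol's Fisher Z interval, state one suited to a tied four-level variable, such as the 5000-sample bootstrap that the SAP already uses for RMSD.
2. Return DAS28 and the seven components to secondary and make SAP 2.5, 4.1.1, 4.1.2, 4.2.1 and the note in 4.2.2 agree. Otherwise, record the change as a departure from the protocol, with its date and reasons.
3. Lesser items: add the baseline TUV_global correlation rows. Either tabulate A-against-B RMSD at 60 and 180 minutes with the final TUV definition, or state that the Interim Analysis 3 results are final and used the final metric and all Arm 1-2 subjects.

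The cost is SAP wording, two ACR rows per reader in Tables 19-20, the baseline rows, and one table pair or one sentence on precision. No further data collection is needed.

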4.1.2 Secondary efficacy variables

- Qualitative evaluations of SPECT/CT image detecting localization of Tc 99m tilmanocept in the synovial spaces of the bilateral hands and wrists. (Arm 2 only).
- CDAI score at baseline (CDAI_{0w}), 12 (CDAI_{12w}) and 24 weeks (CDAI_{24w}) (Arm 3 only).
- ACR Response Criteria at 12 and 24 weeks (Arm 3 only).
- Constituent scores of the ACR Response Criteria at baseline, 12 weeks, and 24 weeks, including:
 - TJC
 - SJC
 - Patient assessment of global disease activity
 - Rheumatologist assessment of global disease activity
 - Patient assessment of pain
 - Patient assessment of physical function
 - Acute-phase reactant value.
- Constituent scores of the CDAI score
 - TJC
 - SJC
 - Patient Global Assessment
 - Physician Global Assessment.

The secondary efficacy endpoints for this study are:

ARMS 1-2

- The temporal stability of TUV_{joint} and TUV_{global} using a 150 mcg tilmanocept mass dose/10 mCi radiolabeling dose, which is defined as the squared difference between the 1-hour and 3-hour planar images. (This endpoint was analyzed to the sponsor's satisfaction in IA-3.)

ARM 1

- The normal upper limit of TUV_{joint} in HC subjects, which is defined the upper limit of a 95% prediction interval at 60 ±15 minutes:
 - TUV_{joint} of evaluated joints (i.e., wrists, MCPs, PIPs, knees, elbows, shoulders in Arms 1 and 2, and wrists, MCPs, and PIPs in Arm 3).

ARM 2

- The qualitative evaluations of SPECT/CT in detecting localization within synovial spaces of the bilateral hands and wrists.

ARM 3

- $\text{TUV}_{\text{global}[0w]}$ and response to new anti-TNF α bDMARD therapy defined by the change from baseline (CFB) of CDAI to 12 ± 1 weeks and 24 ± 1 weeks (ΔCDAI_{12w} and ΔCDAI_{24w} , respectively) and by the changes from baseline in each of the ACR Response Criteria components at 12 (± 1) weeks and at 24 (± 1) weeks.
- $\Delta\text{TUV}_{\text{global}[5w]}$ and response to new anti-TNF α bDMARD therapy defined by the CFB of CDAI to 12 ± 1 weeks and 24 ± 1 weeks (ΔCDAI_{12w} and ΔCDAI_{24w} , respectively).
- $\Delta\text{TUV}_{\text{global}[12w]}$ and $\Delta\text{TUV}_{\text{global}[24w]}$.
- Concordance of improvement classification using $\Delta\text{TUV}_{\text{global}[5w]}$ and $\Delta\text{TUV}_{\text{global}[5w]}$ with anti-citrullinated protein/peptide antibody (ACPA) bucketing improvement classification using clinical criteria, including ACR Response Criteria, CDAI, DAS28, and HAQ-DI. See section 4.2.2 below for the definitions of improvement on these clinical criteria.
- Concordance of improvement classification using $\Delta\text{TUV}_{\text{global}[12w]}$ and $\Delta\text{TUV}_{\text{global}[12w]}$ with ACPA bucketing improvement classification using clinical criteria, including ACR Response Criteria, CDAI, DAS28, and HAQ-DI.
- Response to new anti-TNF α bDMARD therapy defined by the CFB of CDAI to 12 ± 1 weeks and 24 ± 1 weeks (ΔCDAI_{12w} and ΔCDAI_{24w} , respectively).
- The correlation of $\Delta\text{TUV}_{\text{global}[5w]}$ and response to new anti-TNF α bDMARD therapy from baseline to 24 ± 1 weeks defined by the changes from baseline in each of the ACR Response Criteria components.
- Constituent parameters of CDAI_{12w} , CDAI_{24w} , ΔCDAI_{12w} , ΔCDAI_{24w} , ACR Response Criteria at 12 and 24 weeks, including:
 - TJC
 - SJC
 - Patient assessment of global disease activity
 - Rheumatologist assessment of global disease activity
 - Patient assessment of pain
 - Patient assessment of physical function
 - Acute-phase reactant value.

4.2 Analysis of Efficacy Variables

4.2.1 Primary Efficacy Variables

Primary Endpoints for Arms 1 and 2

All TUV data will be analyzed with summary statistics (mean, standard deviation, n, minimum, median, maximum) by study arm and joint.

Precision endpoints will be assessed estimating the mean, standard deviation, n, minimum, median, and maximum of the signed differences (CFB). The RMSD will be calculated

$$RMSD = \frac{1}{n-1} \sum_{k=1}^n (y_k - w_k)^2$$

where y_k and w_k are the measurements at the two timepoints and k represents the subject number. A 95% confidence interval for the RMSD based on Normal theory will be provided, as will a 95% bootstrap confidence interval based on $N = 5000$ bootstrap samples. Timepoints analyzed in this way will include the 60 minute A and B scans, the 180 minute A and B scans, and the difference between the 60 and 180 minute A scans. These will be done for all joints assessed and for TUV_{global} . (These analyses were completed to the sponsor's satisfaction in IA-3.)

Primary Endpoint for Arm 2 Only

The longitudinal (8-day) variation of TUV will be analyzed for each DAS28 joint and globally. The signed differences will be analyzed with descriptive statistics and the RMSD will be calculated as defined for Arm 2 above. A 95% confidence interval for the RMSD based on Normal theory will be provided, as will a 95% bootstrap confidence interval based on $N = 5000$ bootstrap samples will be computed, and 95% confidence limits for its value will be provided. This will be done for TUV_{joint} for all evaluated joints and TUV_{global} in the 60 minute images using the "A" image at baseline. The fraction of unsigned ΔTUV_{global} values less than 7.5% will be summarized in a frequency table and an exact binomial test of the hypotheses described in Section 1.3 will be included for each timepoint.

Primary Endpoints for Arm 3 Only

The Kendall rank correlation between $\Delta TUV_{global[5w]}$ with $\Delta CDAL_{12w}$ and $\Delta CDAL_{24w}$ will be computed and a 95% confidence interval for its value will be computed using Fisher's Z-transformation. Similarly, the Kendall rank correlation between $\Delta TUV_{global[5w]}$ with changes from baseline in DAS28 and in each of the ACR Response Criteria components at weeks 12 and 24 will be computed and a 95% confidence interval for its value will be computed using Fisher's Z-transformation. The marginal distributions of the variables will be characterized with the mean, standard deviation, and the number of data pairs.

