Precision endpoints for both arms will be assessed estimating the mean, standard deviation, n, minimum, median, and maximum of the signed differences (change from baseline) of TUV for each evaluated DAS28 joint. The RMSD will be calculated using the following equation:

$$RMSD = \sqrt{\frac{1}{n-1} \sum_{k=1}^n (y_k - w_k)^2}$$

where y_k and w_k are the measurements at the two timepoints (for example, the two scans at 60 minutes, the two scans at 180 minutes, or the first 60-minute scan and the first 180-minute scan) and k represents the subject number. A 95% confidence interval for the RMSD based on Normal theory will be provided, as will a 95% bootstrap confidence interval based on $N = 5000$ bootstrap samples. Box-and-whisker plots of TUV will be provided by arm at each timepoint for each joint, pooling small joints (MCPs and PIPs) and all joints bilaterally. Joints will not be pooled by type or bilaterally in IA 3.

ΔTUV will be summarized with descriptive statistics as the signed difference. If T_1 represents the observed TUV at the first time point and T_2 the observed TUV at the second time point, then

$$\Delta TUV = T_2 - T_1.$$

Arm 1 Only:

The distribution of TUV_{joint} in healthy controls will be summarized by time point for global TUV and each evaluated DAS28 joint with the number of joints, mean, standard deviation, 80th and 90th percentiles, the median, and 95% prediction limits for a future observation of that type at that time point. Joints will not be pooled. Box-and-whisker plots of the data will be presented by joint and time point. A scatter plot matrix for the three readers will be provided on a joint-specific basis showing the relationship between the reader TUV for the A and B scans.

Arm 2 Only:

The longitudinal precision of TUV_{joint} will be analyzed for each evaluated DAS28 joint. The signed differences will be analyzed with descriptive statistics and the RMSD will be calculated as defined for Arms 1 and 2 above. A 95% confidence interval for the RMSD based on Normal theory will be provided, as will a 95% bootstrap confidence interval based on $N = 5000$ bootstrap samples. Joints will not be pooled by type or bilaterally. A scatter plot matrix for the three readers will be provided on a joint-specific basis showing the relationship between the reader TUV for the A and B scans.

Arm 3 Only:

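### Protocol 9.5.3.1 analyses a primary endpoint with the CV of scan differences, where the endpoint is the CV of TUV; the promised RA-versus-HC CV comparison is missing from SAP 4.2.1 and Table 13; and SAP 4.2.1 prints RMSD without its root

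*SAP*

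**What the plan says.** **CV endpoint.** The protocol (synopsis and 9.3) and SAP 4.1.1 define stability of the mean/variance relationship as a comparison of the CV of TUV_joint and TUV_global between active RA subjects and healthy controls.

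**CV analysis.**
- Protocol 9.5.3.1: "Stability of the mean/variance relationship will be assessed by the coefficient of variation of the differences for active RA subjects and HC subjects", at 60 and 180 minutes. It then promises "95% confidence intervals for the difference in CVs following the methods of" a cited Normal-theory paper (Forkman), plus a bootstrap interval from 5000 samples.
- Protocol synopsis, Statistical Methods: a 95% interval for the RA-versus-HC difference in CV at each time point. The Forkman interval is given only if both groups have a CV below 0.30, and the bootstrap interval always.
- SAP 4.2.1: no mention of CV. Forkman appears in the SAP only in the reference list.
- SAP Table 13 shell: a CV and two intervals for HC, and the same for RA-2, in separate rows.
- SAP Introduction: the SAP is declared consistent with Amendment 4.

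**RMSD.** SAP 2.5 prints "RMSD = \sqrt{\frac{1}{n-1} \sum_{k=1}^n (y_k - w_k)^2" (closing brace omitted here) and says of the Arm 2 longitudinal analysis that "RMSD will be calculated as defined for Arms 1 and 2 above". SAP 4.2.1 prints "RMSD = \frac{1}{n-1} \sum_{k=1}^n (y_k - w_k)^2" and says of the eight-day analysis that "RMSD will be calculated as defined for Arm 2 above". The paragraph on the 60- and 180-minute scans in 4.2.1 ends with "These analyses were completed to the sponsor's satisfaction in IA-3". The eight-day paragraph has no such remark.

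**The concern.** The CV of TUV describes how spread scales with level, which is what the endpoint is about. The CV of the differences divides the SD of the scan-to-scan change by its mean. In a precision study that mean should be close to zero, so the ratio is least stable when the imaging performs best.

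Three literal readings lead to three different outputs:
- Following protocol 9.5.3.1 gives an unstable ratio that does not describe TUV.
- Following the Table 13 shell gives the right CV, but not the promised difference between groups.
- Following SAP 4.2.1 gives a mean squared difference under the label RMSD, including for the eight-day primary endpoint, which is not marked as completed.

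**Working it through.** The documents give no TUV mean, SD or scan bias and no figure that rests on RMSD or CV, so there is nothing to reproduce. The inputs taken from the plan are n = 38 per arm (SAP 1.3) and the 0.30 condition (protocol synopsis). The rest is assumed and labelled so.

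**1. Size of the CV of differences.** Let d̄ and s be the mean and SD of the differences in one arm. CV = s/d̄ and T = d̄/(s/√38), so CV = √38/T = 6.164/T. With Normal differences and zero true mean, T follows Student's t with 37 df.
- Median absolute CV: 6.164/0.681 = 9.05, where 0.681 is the 75% point of t.
- Upper 97.5% point: 6.164/0.0631, about 98, where 0.0631 is the 52.5% point of t. By symmetry the lower limit is about -98, and half of all CVs are negative.

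With a non-zero mean difference (simulated, Normal differences):

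| True mean difference, in SDs | Median absolute CV | Central 95% range of CV |
|---|---|---|
| 0.2 | 4.9 | about -42 to +49 |
| 0.5 | 2.0 | 1.1 to 5.4 |
| 1 | 0.99 | 0.68 to 1.54 |
| 2 | 0.50 | 0.37 to 0.65 |

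**2. The 0.30 condition.** A positive CV below 0.30 needs T above 6.164/0.30 = 20.5. From the noncentral t, the chance in one arm is 3e-10 at a mean difference of 1 SD, 0.0005 at 2 SD and 0.23 at 3 SD. For two independent arms at 3 SD it is 0.23 × 0.23 = 0.05. On the difference scale the condition would almost never be met, so the synopsis rule makes sense only for the CV of TUV.

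**3. The group comparison.** For two identical arms of 38, the middle half of RA-minus-HC results runs from about -17 to +17 for the CV of differences at zero bias. For the CV of TUV it is -0.023 to +0.023 at an assumed CV of 0.20, and -0.067 to +0.067 at 0.50.

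**4. Separate intervals do not replace the difference.** The large-sample standard error of a CV is CV × √(1/(2 × 37) + CV²/38). Assume 0.20 in HC and 0.29 in RA:
- HC: SE 0.0241, interval 0.153 to 0.247.
- RA: SE 0.0364, interval 0.219 to 0.361.
- Difference: 0.09 ± 1.96 × √(0.0241² + 0.0364²) = 0.004 to 0.176.

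The two arm intervals overlap, yet the interval for the difference excludes zero. A reader of Table 13 could not recover the promised result by eye.

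**5. RMSD.** The 4.2.1 expression is the square of the 2.5 expression. For illustration at n = 38, with chi-square limits on 37 df, an RMSD of 0.05 (0.041 to 0.065) would print as 0.0025 (0.0017 to 0.0042), and 2.0 would print as 4.0. The sum of squares is not centred, so with zero bias 38 df is the closer choice. It gives 0.040 to 0.064, which changes nothing of substance.

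**6. TUV_global in healthy controls.** The CV comparison needs HC values, and the SAP is divided on whether TUV_global has them. The calculation steps in 2.5, the first list in 4.1.1 and the footnote to Data Listing 27 confine it to the RA arms. The Arm 1 paragraph of 2.5, the camera-precision and CV items in 4.1.1, the temporal-stability endpoint in 4.1.2, and the Arms 1 and 2 analyses in 4.2.1 and 4.2.2 include Arm 1. Section 4.1.1 therefore contradicts itself.

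**The case against.** **The CV wording is one stray phrase.** The endpoint definitions, the synopsis and Table 13 all point to the CV of TUV, so an analyst would probably compute that, and the extreme ranges above arise only if 9.5.3.1 is followed literally. This stands as a limit on the likely damage. But 9.5.3.1 is the protocol's detailed statement of this analysis, and its preceding paragraph concerns signed differences, so the literal reading is a natural one.

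**The comparison is missing only from the SAP.** This is correct: the protocol names the interval, the cited method and the bootstrap, and the interim analysis plans are not among the documents. But Table 13 is listed as a final table, and the IA-3 completion remark follows a paragraph that does not mention CV.

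**The time-point column may be a conversion loss.** Table 13 is titled by time point but shows no such column in the available text. The source shell must be checked before this counts as an omission.

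**The RMSD form is already settled.** This objection succeeds. A reader might take the SAP 4.1.2 endpoint, "which is defined as the squared difference between the 1-hour and 3-hour planar images", as a sign that squared units are intended. It does not support that: it defines a different, secondary endpoint and does not define RMSD. The name Root Mean Square Difference and SAP 2.5 settle the matter.

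**Conclusion.** The point holds, chiefly for the CV. Protocol 9.5.3.1 contradicts the endpoint that it analyses, and the promised RA-versus-HC interval has neither a method in SAP 4.2.1 nor a place in the Table 13 shell. The figure of about 9, with a range of about -98 to +98, rests on n = 38, Normal differences, zero mean difference and a literal reading of 9.5.3.1. It shrinks as the mean difference grows.

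The missing root is a lesser matter of notation, possibly only a conversion loss.

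A reader might infer that the study's hypothesis test or sample size is affected, or that the IA-3 results are wrong. The documents support neither. The Arm 2 test uses the fraction of differences under 7.5%, no threshold rests on RMSD or CV, and nothing shows which formula IA-3 used. This should be fixed before the final analysis, but it does not undermine the design.

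**What to change.** 1. **Protocol 9.5.3.1:** replace the CV of the differences with the CV of TUV, by arm, at 60 and 180 minutes.
2. **SAP 4.2.1:** state the RA-minus-HC difference in CV at each time point, with the 5000-sample bootstrap interval. Decide explicitly whether the Forkman interval is conditional on both CVs being below 0.30 (synopsis) or unconditional (9.5.3.1).
3. **Table 13:** add a difference row and, if the source shell lacks one, a time-point column.
4. **RMSD:** check the source file for a lost radical, print the rooted formula of SAP 2.5 in 4.2.1, and confirm which form IA-3 used. If it was unrooted, take the root of the estimates and of chi-square or percentile-bootstrap limits. Recompute any other type of bootstrap limit on the RMSD scale, because rooting is not valid for every type and the SAP does not name the one used.
5. **Separately,** decide whether TUV_global is computed for healthy controls, align the SAP sections listed above, and let items 1 to 3 follow that decision.

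The cost is wording, one check of the source file and the IA-3 programs, and a small table change. Item 1 alters a primary analysis, so it needs a formal amendment under protocol 3.2. The SAP edits need the change order described on its approval page. No new data are required.
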